Specifically, we aim to investigate the neurobiological mechanistic response of women to memory enhancement training (MET) compared to combined Kundalini yoga (KY) and Kirtan Kriya (KK, a Kundalini yoga meditation) through a randomized study targeting women with high AD risk. For the purposes of this study, women with high risk for AD are defined as women with high cardiovascular risk (Ho, Pinsky, Kannel, & Levy, 1993; Truelsen, Lindenstrom, & Boysen, 1994) and subjective memory complaints. The methodology for this study is based on our study of individuals with MCI randomized to either combined KK+KY or to memory enhancement training (MET) (B. P. Acevedo et al., 2016; Eyre et al., 2016; Eyre et al., 2017; H. Yang et al., 2016). Compared to MET, KK+KY demonstrated short- and long-term benefits in executive functioning, as well as broader effects on depressed mood and resilience. The positive outcomes of this study suggest that KK+KY may be a promising intervention for reducing risk for AD in women. Our study sample will consist of 100 women over the age of 50 with high risk of developing AD. Participants will be randomized to 12 weeks of either KK+KY or MET. The primary outcome is memory performance. Secondary outcomes include executive functioning, brain structure and connectivity. The benefit of interventions will be determined at 12 weeks and at 6- and 12- month follow-up. The proposed study will test the mechanisms and efficacy of the proposed interventions to improve memory and cognitive performance, mood, resilience and quality of life in older women, with the purpose of reducing AD risk in this population. We will use the proposed model to develop preventive interventions for women at high-risk for developing AD.

Introduction:

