We designed the present randomized trial to test whether 12 weeks of supervised weekly Kundalini yoga class and a brief daily home meditation practice can improve cognitive function among older women with high AD risk compared to weekly classes of memory training with daily homework. Our choice of interventions is based on prior studies of mind-body exercise in older adults that revealed robust cognitive benefit, as well as our own studies of this intervention compared to cognitive memory training in older adults with MCI. Kundalini yoga has also been observed to impact the frontal lobes, likely due to increased cerebral blood flow ([name] et al., 2013b).

The primary outcome will be memory performance at 12 weeks (i.e., immediately post-treatment).

Secondary outcomes include measures of executive functioning and changes in brain structure and connectivity.

Specific Aim 1: To evaluate effects of Kundalini Yoga+ Kirtan Kriya (KK+KY) and Memory Enhancement Training (MET) on memory performance in women with high AD risk.

Hypothesis 1: Improved memory performance will be observed in women receiving KK+KY and MET at 12 weeks compared to baseline.

Specific Aim 2: To test the efficacy of KK+KY vs. MET for improving executive functioning including working memory.

Hypothesis 2: KK+KY will improve performance in executive functioning to a greater extent than MET.

Exploratory Aim 3a: To test the effects of MET vs. KK+KY on structural and functional connectivity and task-related activation for working and episodic memory.

Hypothesis 3a: Compared to MET, KK+KY will be associated with greater improvement in connectivity in regions associated with working and episodic memory.

Exploratory Aim 3b: To test the effects of MET vs. KK+KY on levels of cellular and genomic markers of inflammation, telomerase activity level, and telomere length after 12 weeks and at 6 and 12 month follow-up.

Hypothesis 3b: Compared to MET, KK+KY will be associated with decreases in cellular and genomic markers of inflammation and increases in telomerase activity level and telomere length after 12 weeks and at 6 and 12 month follow-up.

Exploratory Aim 3c: To explore whether KK+KY results in reduced cardiovascular risk factors compared to MET, and whether this effect will correlate temporally with changes in fMRI measures and clinical outcomes.

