Microarray-based genome-wide transcriptional analyses will be used identify the molecular inflammation-related signaling pathways that are plausible candidates for molecular mediators of inflammation (e.g., NF-B) (Cole, 2010; Irwin, Olmstead, & Motivala, 2008; Irwin, Wang, Campomayor, Collado-Hidalgo, & Cole, 2006) and

glucocorticoid receptor-related signaling pathways that may underlie increased inflammatory signaling (Cole et al., 2007; G. E. Miller et al., 2008) with measures performed at baseline, week 12, and at 6months, as described previously (Cole et al., 2007; G. E. Miller et al., 2008). Expression data will be subject to quantile normalization, with differentially expressed genes identified based on False Discovery Rate analyses controlling false positive errors at 5%, and subsequent TELiS bioinformatics analysis of GR target motifs within the promoters of genes up-regulated in KK+KY vs. MET. Confirmatory RT-PCR analyses will be conducted on a subset of 12 differentially expressed transcripts to confirm microarray indications (Cole et al., 2007; G. E. Miller et al., 2008). We will assess the activity of telomerase level and TL at baseline, weeks 12 and 6month follow-up to monitor changes. The protocol will be the same as the one used previously by Jacobs and colleagues (Jacobs et al., 2011). Quantification of telomerase activity will be measured from the extract using the telomeric repeat amplification protocol (TRAP) as previously described (Kim & Wu, 1997) with a commercial kit (TRAPeze®, Chemicon, Temecula, CA). We will assess other factors related to inflammation during our baseline assessment and throughout the trial (e.g., alcohol, smoking, BMI, physical activity; use of NSAIDs, and recent infections when samples are

		•	
Sequence #	Sequence type	Acquisition time	Protocol type
	1. Localizer		-21: -
1.1	Localizer	0:00:09	HCP
1.2	AAHScout	0:00:14	HCP
1.3	Localizer_aligned	0:00:21	HCP
	2. T1-weighted image)	
2.1	T1w setter	0:00:02	HCP
2.2	T1w MPR vNav 4e	0:08:22	HCP
	3. T2-weighted image)	
3.1	T2w setter	0:00:03	HCP
3.2	T2w_SPC_vNav	0:06:35	HCP
	4. Resting state fMR		
4.1	SpinEchoFieldMap_AP	0:00:09	HCP
4.1	SpinEchoFieldMap_PA	0:00:09	HCP
4.3	Cal_800TR	0:00:30	HCP
4.4	rfMRI_REST_AP	0:06:41	HCP
4.5	rfMRI_REST_PA	0:06:41	HCP
	5. tfMRI N-back task		
5.1	task fMRI N-back	010:00	HCP
5.2	SpinEchoFieldMap_AP	0:00:09	HCP
5.3	SpinEchoFieldMap_PA	0:00:09	HCP
	6. task fMRI face nami	ng	
6.1	task fMRI face naming	0:05:25	HCP

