Data will be analyzed using the SAS (v9.4) statistical package. Data will be examined initially to identify issues such as departures from normality, which might suggest the need for transformation (e.g., logarithmic). Demographic variables (e.g., age, gender, etc.) will be compared by treatment group and examined in relation to outcome variables; this would define one possible set of appropriate covariates, if needed. Correlations (a) among outcome measures and (b) among potential covariates will be examined to eliminate redundancy via possible data reduction, e.g., formation of composite scores or selection of single measures from sets of highly inter-correlated variables. Cognitive domain scores will be obtained as follows: for each neuropsychological test, raw scores will be converted to standardized (Z) scores with a mean of 0 and a SD of 1, based on all participants combined. Then, for each of the tests in a cognitive domain, the Z scores will be averaged to create a single Z score per cognitive domain.

The independent samples *t*-test or Chi-square test will be used to compare the demographic characteristics between the MET and KK+KY control group. The effect of intervention over time on the cognitive functions will be investigated in intention-to-treat (ITT) analyses. Measurements will be analyzed using linear mixed models; analyses will assume missing at random with missingness allowed. All models will include random intercepts to account for correlations between the repeated measures for each participant. The fixed components of the models will include effects of group and time and a group X time interaction, with post hoc analyses between times and groups. All statistical significance tests will be two-sided, and an alpha-level of 0.05 will be considered statistically significant for primary analyses and Bonferroni correction will be employed for post hoc analyses.

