Primary outcome: The analyses for the memory domain Z scores will use general linear mixed model (GLMM) analysis (e.g., SAS PROC MIXED). The two treatment groups will be compared for time course of cognitive domain z scores the initial endpoint EOT at 12 weeks and 6- and 12-months. Covariates may be included in the model as noted above. As noted above, the primary cognitive domain of interest for this proposal is memory. A separate GLMM as above will be estimated using memory domain z-scores as dependent variables. Executive Function will be examined as secondary outcome measure. Supplementary analyses of the follow-up period will look at the cognitive domain scores by treatment group controlling for values at EOT (post-treatment changes). Objective memory measures will be examined using a similar GLMM.

Exploratory Hypotheses: GLMM models as described above will be used to examine telomerase activity (overall level and TL) and inflammatory measures separately. Relationships between changes in markers of inflammation and telomerase activity to changes in cognitive scores, cognitive domain scores and fMRI measures will be examined using regression models within each group. Transformations of the measures will be performed as necessary.

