Power analysis: The power analysis is focused on the primary aim of the study to assess whether the KK+KY and MET groups demonstrate comparable improvement in memory performance. We plan to enroll a total of 100 women in the study, anticipating an attrition rate of at most 10% based on our previous studies. Thus, we will most likely have a total of 90 completers. With a sample size of 45 per group, we achieve 80% power to detect equivalence within a margin of equivalence of 0.62, when the true difference between the means is assumed to be zero. In the PI's previous study using similar interventions on older adults with MCI, a between-group effect size of 0.3-0.4 was observed for the memory measures. In the proposed study, the target population is women with high risk for AD, hence we believe that the proposed sample size will have sufficient power to address the primary hypothesis of the study. With this sample size, we can also expect to detect an effect size of 0.60 at a significance level of 0.05 and 80% power for the secondary outcome measure (executive functioning). We intend to test the secondary outcomes adjusting for multiple comparisons using the Benjamini-Hochberg false discovery rate approach (which is more powerful than the simple Bonferroni correction). Further, we will report results of all proposed analyses and conclusions will be based on the pattern of results.

Data management: Data management and analysis support will be provided by the UCLA Semel Institute Statistical Core (SI-Stat) ([name]). The SI-Stat will provide needed software and technical support with a data manager operating under the supervision of [name]. The SI-Stat has a Dell PC computer network with

automated CD R/W backup and is set up for medium to large-scale data processing and analysis using available commercial database and statistical software. **1. Randomization.** Randomization schedules will be prepared in a masked manner by the statistician. **2. Data submission and quality control.** Data forms will be delivered from the originating location to the central data unit within one week of being generated. When errors, omissions, or unclear information is detected on the paper forms, a copy will be returned for corrections. The data manager will generate monthly reports summarizing missing and incorrect data will be sent to the PI.

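### Imaging is labelled both secondary, which brings Benjamini-Hochberg control, and exploratory, with no stated control; the 80% power for executive function holds only if it is tested alone

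*Combined protocol and SAP*

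**What the plan says.** **Imaging as secondary.** The Abstract states: "Secondary outcomes include executive functioning, brain structure and connectivity". The outcome list just before the Specific Aims repeats this; the secondary outcomes "include measures of executive functioning and changes in brain structure and connectivity".

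**Imaging as exploratory.** A few lines later, Aim 3a, the first of the exploratory aims, is worded as follows: "To test the effects of MET vs. KK+KY on structural and functional connectivity and task-related activation for working and episodic memory". Its hypothesis is directional and favours KK+KY.

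**Rule for secondary outcomes.** The Power analysis section says: "We intend to test the secondary outcomes adjusting for multiple comparisons using the Benjamini-Hochberg false discovery rate approach". It lists neither the members of the family nor the false-discovery level. The same section gives a detectable effect of 0.60 for executive functioning at significance level 0.05 and 80% power, with 45 per group.

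**Rule for exploratory outcomes.** The Exploratory Hypotheses paragraph says: "GLMM models as described above will be used to examine telomerase activity (overall level and TL) and inflammatory measures separately". It mentions fMRI only in regressions within each group and states no correction.

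**Corrections stated elsewhere.** For gene expression there is a 5% rule: "differentially expressed genes identified based on False Discovery Rate analyses controlling false positive errors at 5" percent. For the mixed models, "Bonferroni correction will be employed for post hoc analyses". Neither is said to cover imaging. The imaging sections, from Functional Imaging to Integration with Mood and Neurocognitive Measures, give no voxel, cluster or false-discovery threshold for the trial's group comparisons. The FDR wording in the Figure 6 caption belongs to an ECT illustration.

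**The concern.** The label decides the rule. If imaging is secondary, it enters a Benjamini-Hochberg family with executive function, and the number and strength of the imaging results affect the threshold that executive function must meet. Hypothesis 2, on executive function, is the plan's only directional between-group hypothesis on cognitive test performance, so this matters. If imaging is exploratory, no stated rule limits chance findings, yet a positive result could still be reported under the secondary label used in the Abstract and the outcome list. The plan does not say which label governs, and its power statement takes no account of the adjustment announced in the same section.

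**Working it through.** **Inputs from the plan:** 45 completers per group, effect 0.60 SD, two-sided 0.05, 80% power (Power analysis; Data analysis).

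**Assumptions, because the plan is silent:** false-discovery level 5%; number of imaging tests varied from one to fourteen; normal approximation.

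Fourteen is an illustrative count built from the imaging sections. Five resting networks (default mode, executive, salience, fronto-parietal, dorsal attention), plus three seeds (hippocampus, ACC, DLPFC) under three task conditions (2-back against 0-back, learned against novel pairs, encoding), give 5 + 3 × 3 = 14. No such number appears in the plan.

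**Step 1. Reproduce the plan's figure.** The expected z is 0.60 × √(45/2) = 2.846. Power for one test at 0.05 is Φ(2.846 − 1.960) = Φ(0.886) = 0.81. With the exact noncentral t it is 0.804, and the detectable effect is 0.597. The stated 0.60 is therefore right for a single unadjusted test.

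**Step 2. Executive function in a Benjamini-Hochberg family with c null companions.** The procedure always rejects a p-value at or below 0.05/(c + 1), so power is at least Φ(2.846 − z), where z is the two-sided critical value at that level. Simulating the full step-up procedure gives slightly more.

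| Null companions c | Level 0.05/(c + 1) | z | Lower bound | Simulated power |
|---|---|---|---|---|
| 0 | 0.0500 | 1.960 | 0.81 | 0.81 |
| 1 | 0.0250 | 2.241 | 0.73 | about 0.73 |
| 2 | 0.0167 | 2.394 | 0.67 | about 0.68 |
| 4 | 0.0100 | 2.576 | 0.61 | 0.61 to 0.62 |
| 5 | 0.0083 | 2.638 | 0.58 | about 0.59 |
| 14 | 0.0033 | 2.935 | 0.46 | about 0.47 |

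With fourteen null companions the result stays near 0.47 whatever the correlation tried.

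**Step 3. The opposite extreme.** If all fourteen companions also have a 0.60 SD effect and the tests are independent, power for executive function is about 0.78. In the same family of fifteen, it is about 0.56 with three real effects and 0.70 with eight.

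**Step 4. Imaging uncorrected at 0.05, all nulls true (assumed reading).** For fourteen independent tests, the chance of at least one false positive is 1 − 0.95^14 = 0.51. By simulation it is about 0.35 at correlation 0.5 and 0.20 at 0.8. For five tests it is 1 − 0.95^5 = 0.23 if independent and about 0.13 at correlation 0.8.

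**The case against.** Several counter-arguments have force.

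- **The analysis text leans towards one reading.** The Neuropsychological tests paragraph, the Primary outcome paragraph and the Power analysis each name executive functioning, in the singular, as the secondary outcome measure. A shared family with imaging is therefore the less natural reading. This points to the fix but leaves the two secondary lists that include imaging in place.
- **The trial is called a pilot, and the plan promises to report all analyses and judge the overall pattern.** That limits selective reporting. It does not limit chance findings.
- **A shared Benjamini-Hochberg family is not an error in itself.** This stands. The fault is that the family is undefined and the power statement ignores it.

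A reader might also draw stronger conclusions that the documents do not support:

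- *Imaging will be tested at an unadjusted 0.05.* The plan attaches 0.05 to the primary analyses and gives no imaging threshold. The 20% to 51% describes one reading only. The seed analyses produce whole-brain maps, so fourteen single tests are a simplification.
- *Power for executive function is 47%.* That requires fourteen imaging tests in its family, all of them null, whereas Hypothesis 3a predicts effects.
- *Exploratory outcomes have no error control at all.* Gene expression under Aim 3b has a 5% false-discovery rule.
- *The secondary item and Aim 3a cover identical measures.* Connectivity is in both. Brain structure in the sense of volume, thickness and shape is not in Aim 3a as worded.
- *Removing imaging alone restores 80%.* The plan also names secondary clinical outcome measures. With the four in that paragraph (CGI, Memory Functioning Questionnaire, BDI, Hamilton Anxiety) as null companions, power is still only about 61% to 62%.

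**Conclusion.** The conflict is real and lies in current text: connectivity is both secondary and exploratory, and the two labels lead to different decision rules for the same result. The stated 80% power for executive function is correct only for a test on its own at 0.05. At an assumed 5% false-discovery level with 45 per arm, sharing a family with imaging lowers it to about 73%, 59% or 47% with one, five or fourteen null companions. The loss nearly disappears, at about 78%, if all fourteen companions have effects of the same size. The false-positive range rests further on the assumed number of tests, their correlation and an assumed 0.05 threshold. The inconsistency and the single-test basis of the power figure do not depend on these assumptions. The matter should be settled before analysis.

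**What to change.** Give imaging one label.

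1. In the Abstract and in the outcome list before the Specific Aims, remove brain structure and connectivity from the secondary outcomes. This agrees with the sections that name executive functioning as the secondary outcome measure.
2. Reword Exploratory Aim 3a to include brain structure, which would otherwise fall under no aim. State that imaging is hypothesis-generating and has its own separate false-discovery family.
3. In Power analysis, choose one of two courses. Either test executive function outside any family shared with imaging or the other clinical outcomes, so that the stated 80% holds. Or, if the clinical outcomes share its family, list the members and the false-discovery level and restate the power (61% to 62% at 0.60 SD with four null companions and a 5% level).

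The cost is wording in a few places, with no new data, visits or participants. The price is that an imaging result can no longer be presented as a secondary-outcome success and, under the second course, that the stated power is less favourable.

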Memory Enhancement Training (MET): Memory training is based on the notion that cognition is plastic in older age (A. Acevedo & Loewenstein, 2007). Traditional memory training interventions facilitate plasticity by teaching people mnemonic techniques involving verbal association and visual imagery and practical strategies that boost encoding and retrieval (Gross et al., 2012; Verhaeghen, Marcoen, & Goossens, 1992). A meta-analysis of 33 clinical trials including data from over 1,500 older adults showed that gains on objective memory tests following memory training are large (i.e. on average, a standardized mean difference from pretest to posttest of .73) compared to the small-medium sized effects for control (.37) and placebo (.38) conditions. A more recent metaanalysis (Gross et al., 2012) of 35 studies reported that memory training effects remain significant after controlling for practice effect. The overall estimate of effect size (the mean standardized difference in pre-post change between memory-trained and control groups) was 0.31 standard deviations (SD); the pre-post training effect for memory-trained interventions was 0.43 SD and the practice effect for control groups was 0.06 SD. Effective mnemonic memory enhancement methods involved visual imagery, verbal associations, story mnemonics, organizational encoding strategies, and the use of multiple techniques, and no specific strategy is better than another (Bjorklund, Schneider, Cassel, & Ashley, 1994; Gross et al., 2012; Stigsdotter & Bäckman, 1989; Verhaeghen et al., 1992; Willis et al., 2006). Benefits from memory training may last from six months to five years (Verhaeghen et al., 1992; Willis et al., 2006). Memory training can transfer to daily life when participants are given homework practice and training in using techniques in daily life and novel situations (McDaniel & Bugg, 2012). Small group interventions, memory education, and relatively short sessions (e.g. 90 minutes or less) are other important components of training programs (Verhaeghen et al., 1992). Memory training also improves subjective memory functioning but effect sizes are smaller (.30) compared to the effect on objective test performance (Floyd & Scogin, 1997). We chose to implement mnemonic methods over computerized memory training programs because the former have a longer history of implementation in aging populations and have more empirical evidence supporting their use in older adults. The MET program in the current proposal includes evidence-based techniques and approaches to facilitate transfer of new knowledge to participants' everyday lives.

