We propose a randomized controlled design for this pilot 12-week trial of the behavioral intervention MET compared to KK+KY for improving cognitive performance and health in women at high risk of AD. We hope to control for nonspecific factors by using a gold standard active control condition that has demonstrated acceptability in this population.

The proposed study will to test whether KK+KY is superior to MET for improving cognitive functioning, health (including cardiovascular factors), and mood in women with high AD risk. All participants will be recruited from the UCLA Women's Cardiovascular Center, UCLA outpatient clinics and the UCLA Longevity Center Program. All participants will be identified as having high AD risk including subjective memory complaints and high cardiovascular risk based on the 2013 ACC/AHA Guideline on the Assessment of Cardiovascular Risk (Goff et al., 2014). Follow up of all enrolled subjects at 6- and 12-months (52 weeks total) will allow detection of any continued cognitive or health benefits.

b) Methods for reducing risk of bias:

Participants will be informed prior to enrollment that they will receive one of two evidence-based interventions for improving memory. Descriptions of the study will be designed to minimize risk of possible between group differences resulting from differences in treatment expectancy. Differences in treatment expectancy/ credibility will be tested for at baseline, week 12, and week 24 as specified below. We will also control for the "instructor" effect if several instructors teach classes. The feasibility of weekly yoga/MET classes and homework time was assessed during previous studies and found reasonable for participants to complete (Eyre et al., 2016; H. Yang et al., 2016). Behavioral raters will be blind to group assignment.

1. Study Population: We anticipate screening about 250 subjects to recruit 100 women with subjective memory complaints and high cardiovascular risk based on the 2013 ACC/AHA Guideline on the Assessment of Cardiovascular Risk. Participants will be recruited from the women's clinics and geriatric clinics at UCLA as well as the UCLA Longevity Center.

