outcome will be an average of the participant's z-scores on three tests. Two of these tests will be of verbal memory tests: 1) the Hopkins Verbal Learning Test (HVLT) (total and delayed recall scores) (Shapiro et al., 1999), and (2) the Wechsler Memory Scale (WMS-IV) (immediate and delayed) and one will be of visual memory (the Rey-Osterreith Complex Figure 3-minute delay recall). The secondary outcome measure of executive functioning will include Trail Making B and Stroop Color-Word Interference tests to estimate mental flexibility and inhibition/adjustment of behavior. Tests of language fluency will include Animal fluency and CFL Letter Fluency to assess strategic searching/organization of verbal knowledge, as well as the Boston Naming Test. The battery will also include measures of attention/ processing speed which are commonly impaired in the geriatric population according to prior research by our group (Schneider, [name], Siddarth, & [name], 2012) and others (Alexopoulos, Kiosses, Klimstra, Kalavam, & Bruce, 2002; Bhalla et al., 2009; Butters, 2004; Favrod et al., 2015; Lockwood, Alexopoulos, & van Gorp, 2002). These tests place significant demand on mental operations that require speed, manipulation and monitoring of information that is in conscious awareness (Trail Making A; Digit Span; Stroop Color and Word). Most of the measures have 2 or 4 alternate forms so that unique forms may be administered to participants during repeat testing. We include both traditional, standardized tests and computerized tests for enhanced sensitivity of the battery to potential intervention effects and so that our results can also be compared with other findings in the literature. In addition to the cognitive outcome measures, we will include the TOPF to estimate pre-morbid cognitive functioning.

Secondary clinical outcome measures will include the Clinical Global Impression- Severity and Improvement scale (CGI)(Busner, Targum, & Miller, 2009) to quantify overall severity and clinical improvement over time (2 min). Subjective memory complaints will be assessed via the 10-item Memory Functioning Questionnaire scale. The Beck Depression Inventory (BDI) (Beck, Steer, & Brown, 1996; Beck, Steer, & Carbin, 1988), a self-assessment scale of depression (5 min), will also be administered, as will the Hamilton Anxiety scale.

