Autonomic nervous system (ANS) and respiratory measures. In order to link genotype and neuroimaging data with respiratory and ANS functioning, we will perform a series of five tests: 1) rest; 2) paced breathing; 3) breath hold; 4) Valsalva maneuver; 5) hand grip. These tasks will provide detailed information about cardiorespiratory functioning. Continuous blood pressure will be assessed using a probe attached to two fingers of the same hand. An additional finger probe will be used to measure the Galvanic skin response (GSR) and chest electrodes will be applied for the electrocardiogram (ECG) and on the hand for an electromyogram (EMG). A respiratory belt around the patient's chest will provide breath rate data and a small probe attached to the cheek will measure changes in face skin temperature. End-tidal CO2 will be measured using a capnometer and spirometry will be used to investigate pulmonary capacity. Verbal instructions will be provided and a computerized task will indicate to the subjects when to begin and end each challenge, for example when to prepare for the breath hold (deep inhale followed by deep exhale and then hold at the top of the next deep inhale). Data will be recorded and time-locked using a BioPac system and associated software, which will also be used to process the data.

Randomization and treatment schedule:

After all screening and baseline test results are reviewed and eligibility criteria are confirmed, patients will sign the informed consent form. Next, participants will be randomized to either MET or KK+KY groups using a computer-generated random assignment scheme, which assigns participants in a 1:1 ratio to each group using a customized module built into the centralized data system. All behavioral raters will be blind to the group assignment, and participants will be asked not to disclose their group assignment to the raters.

Study intervention procedures:

Participants will be randomized to: (1) MET class for 60 minutes per week plus daily homework; or (2) KY class for 60 minutes per week plus daily KK homework. Participants will complete a questionnaire about their treatment expectations after their second class. Follow-up assessments immediately after the intervention (12 weeks) as well as at 24 and 48 weeks will test the effect of the interventions at both short- and long-term follow-up.

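### Hypothesis 1 rests on improvement from baseline in two active arms, so meeting it cannot be credited to either intervention; how easily it could be met without a treatment effect ranges from under 1% to about 95%, depending on which control-group gain in the protocol applies

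*Combined protocol and SAP*

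**What the plan says.** Under Specific Aim 1 the hypothesis is: "Improved memory performance will be observed in women receiving KK+KY and MET at 12 weeks compared to baseline". The comparison is each arm with its own baseline.

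The abstract gives the design: "Participants will be randomized to 12 weeks of either KK+KY or MET". Under Study Design, MET is described as a "gold standard active control condition that has demonstrated acceptability in this population", and the randomisation section says that the scheme "assigns participants in a 1:1 ratio to each group". No untreated or waiting-list arm, run-in or second baseline is described.

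The background section on Memory Enhancement Training cites two meta-analyses. In the first, trained groups showed "a standardized mean difference from pretest to posttest of .73", against smaller gains for "control (.37) and placebo (.38) conditions". The second, described as more recent and covering 35 studies, gives 0.43 SD for trained groups, 0.06 SD for control groups (labelled a practice effect), and 0.31 SD for the difference in pre-post change.

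On retesting, the section on neuropsychological tests says: "Most of the measures have 2 or 4 alternate forms so that unique forms may be administered to participants during repeat testing".

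The Data analysis section specifies a mixed model with group, time and their interaction, two-sided alpha 0.05 for primary analyses, and Bonferroni correction for post hoc comparisons. The Power analysis addresses whether the two arms improve comparably. It gives no power for change within an arm.

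**The concern.** A rise from baseline can come from the intervention, from having taken the tests before, from expecting to do better, or from regression to the mean in women selected for memory complaints. Separating these needs a comparison group or a repeated baseline, and the design has neither for the within-arm change. Randomisation protects the KK+KY versus MET difference, but Hypothesis 1 does not use that difference.

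At stake is the reading of the primary outcome. If both arms rise significantly, Hypothesis 1 is met as written and Aim 1 would support a statement that both programmes improve memory. If the rises are also similar, the comparability analysis would agree. Two effective programmes and two ineffective ones could produce that same picture.

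**Working it through.** **The plan's own figure.** The Power analysis states 80% power for equivalence with 45 per arm, margin 0.62 and true difference zero. Reading the margin in SD units, with two one-sided tests at 0.05 each: n = 2 × ((1.645 + 1.282)/0.62)² = 44.6, rounded up to 45 per arm. The figure reproduces (power 80.5% by the normal approximation). It concerns the difference between arms and says nothing about Hypothesis 1.

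**Inputs for the check**
- n = 45 completers per arm (Power analysis).
- Gain without treatment, g: 0.06 or 0.38 SD (background on MET). The control figure of 0.37 gives nearly the same results as 0.38.
- Baseline to week-12 correlation, r: not in the documents; assumed 0.5, 0.7 and 0.8.
- Two-sided alpha 0.05 in each arm; then 0.025, a Bonferroni correction over two tests. The plan does not state the number of post hoc tests, so two is an assumption.
- g is taken in baseline SD units of the outcome.

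**Formulae.** SD of change = √(2(1 − r)). Noncentrality = g ÷ (SD of change/√45). The one-arm probability is that of a significant improvement in a paired t-test with 44 degrees of freedom. The arms are independent, so the probability for both is the square.

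Example: g = 0.38, r = 0.7. SD of change = √0.6 = 0.775; standard error = 0.775/6.708 = 0.1155; noncentrality = 0.38/0.1155 = 3.29. One arm: 0.896. Both arms: 0.896² = 0.80.

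| Probability that both arms improve significantly, no treatment effect | r = 0.5 | r = 0.7 | r = 0.8 |
|---|---|---|---|
| g = 0.06, alpha 0.05 | 0.3% | 0.5% | 0.8% |
| g = 0.37, alpha 0.05 | 46% | 77% | 94% |
| g = 0.38, alpha 0.05 | 49% | 80% | 95% |
| g = 0.38, alpha 0.025 | 35% | 69% | 91% |

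Counting significance in either direction changes the first row only slightly, to 0.5%, 0.6% and 0.9%.

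**The pilot as precedent.** The MCI trial summarised under Preliminary data reports significant memory improvement in both groups. From its Table 2, week-12 change divided by baseline SD in the KY group is:
- HVLT total: (27.14 − 25.76)/6.20 = 0.22
- HVLT delayed: (9.48 − 9.03)/2.70 = 0.17
- WMS immediate: (22.28 − 17.19)/9.53 = 0.53
- WMS delayed: (6.72 − 5.22)/2.88 = 0.52
- Rey-O 3-minute: (18.90 − 16.01)/5.93 = 0.49

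The mean is 0.39, about the size of the 0.38 placebo gain. The same calculation for MET gives 0.53, 0.44, 0.73, 0.42 and 0.84, mean 0.59. These are rough, because they use summary means and the women measured may differ between visits. They show that a gain of the larger benchmark's size is plausible on these tests; they do not show its cause.

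**Two conditions on the check.** First, it assumes that the memory tests are given at week 12. The assessment schedule (Table 4) and the sentence introducing the battery do not list them then, while the primary outcome requires it; these places need reconciling. Second, the plan does not say which visit supplies the mean and SD for the z-scores. If each visit were standardised separately, the overall mean change would be zero by construction.

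**The case against.** A reader might infer the stronger claim that retest practice alone would usually confirm Hypothesis 1. The documents do not support it. The 0.37 and 0.38 figures belong to control and placebo conditions; the protocol does not call those groups untreated, nor attribute their gains to practice. The one figure that it does call a practice effect is 0.06 SD, from the more recent meta-analysis, and at that size both arms would almost never reach significance together. This objection stands, so the result must be given as a range.

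The planned Bonferroni correction also lowers the probabilities. With six tests, one for each pair of four visits (again an assumption), the figures at 0.38 SD fall to 18%, 49% and 79%. That weakens the word usually further but does not make the risk small.

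Alternate forms help. For baseline against week 12, two forms are enough, so any need to repeat forms at later visits is beside the point. What remains is that forms are claimed only for most measures, and that they do not address placebo response or regression to the mean.

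Finally, the plan already specifies a randomised comparison, measures treatment expectancy, and cites controlled evidence for memory training (0.31 SD over control). All true. But expectancy is measured to compare the arms, the model compares two active arms, and external evidence for memory training does not identify the effect in this trial, least of all for KK+KY. Hypothesis 1 still asserts improvement in each arm without a control.

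**Conclusion.** The point holds as a limit on attribution: whatever the size of the practice gain, meeting Hypothesis 1 cannot be credited to either intervention, because nothing in the design isolates the treatment part of a within-arm change.

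How often it would be met with no treatment effect is much less certain: below 1% if the untreated gain is 0.06 SD, and 49% to 95% if it is 0.38 SD (35% to 91% with a two-test Bonferroni correction). These figures rest on 45 completers per arm, an assumed correlation of 0.5 to 0.8, and external gains that may not carry over to this population and battery. The documents do not settle which gain applies. The wording should be changed before analysis; the randomised comparison itself is not undermined.

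**What to change.** - Reword Aim 1 and Hypothesis 1 so that change from baseline within each arm is descriptive, and say explicitly that it is not attributed to either intervention.
- Report each arm's standardised pre-post change with its 95% confidence interval beside both benchmarks, 0.06 SD and 0.37–0.38 SD. Name the visit used for standardisation.
- Do not use 0.38 as a pass/fail limit. An arm with a true gain of 0.43 SD, the trained-group figure in the more recent meta-analysis, would have a lower confidence limit above 0.38 only about 5% to 7% of the time at n = 45 and r = 0.5 to 0.8. The observed gain would have to exceed 0.38 + 2.015 × standard error, that is 0.68 SD at r = 0.5 and 0.57 SD at r = 0.8.
- Base efficacy conclusions on the randomised KK+KY versus MET contrast, and state that similar rises in the two arms do not by themselves show that either works.

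The cost is a few sentences in the protocol and one reporting line, with no new data. The price is a weaker claim under Aim 1, and the benchmarks are external and approximate.
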